7.0 Statistical Considerations

As this is not a comparative study, only descriptive statistics will be applied.

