### INTUBATION

King Vision aBlade size:    1    2    2 channeled	Standard laryngoscope blade size:    0    1    2    3
Endotracheal tube size:    2.5    3.0    3.5    4.0    4.5    5.0    5.5    6.0	Brand: _____
Blade tip position:    In vallecula    Under epiglottis	Stylet used:    Yes    No
Ease of ETT passage:    1    2    3    4    5    (1 = very easy; 2 = easy; 3 = neutral; 4 = difficult; 5 = impossible)	
Number of insertion attempts:    1    2    3    (Entry of blade into patient's mouth without the need to remove it once entered)	
Insertion time: _____ (Amount of time from Removal of facemask to the first upstroke of etCO 2 )	
Insertion Technique:  Rotated blade in from side (check all that apply)  External laryngeal manipulation  Rotate ETT counterclockwise (channeled only)  Other: _____	

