laryngoscope introduced into clinical practice was the Glidescope (Verathon Medical, 2003).² Since the introduction of video laryngoscopes most anesthesia departments and critical care departments, including ours, have had a steady increase in the use of video laryngoscopes in place of conventional laryngoscopes.^{3,4,5} Many anesthesiologists now use video laryngoscopes as their standard laryngoscope. Video laryngoscopy is also included in current guidelines for difficult tracheal intubation.⁶ Other video laryngoscopes in clinical use throughout the world include the CMAC (Kart Storz Imaging), Tru-View (Truphatek), McGrath (Covidien), Pentax AWS (Pentax), and the King Vision (Ambu). Some of these devices have pediatric sized blades and some do not.

Processing, portability, and cost are important aspects of video laryngoscope selection. Some devices have patient contact components that are disposable, while other devices are reusable and require processing for sterilization or high-grade disinfection. Patient cross-contamination with potentially infectious material is an increasing concern with reusable airway devices.⁷ Cost is always a concern. Some video laryngoscopes require a separate stand and monitor, and reusable blades. The initial capital outlay for such reusable devices can be as high as \$35,000. The initial financial outlay for the King Vision is \$1500.

The King Vision video laryngoscope was introduced into clinical practice in 2011. The King Vision video laryngoscope is an FDA Device Class CCW instrument that is 510(K) exempt: regulation number 868.5540. This device

consists of a reusable, imaging wand that is inserted into a disposable blade (size 3). Published reports have documented the value of the King Vision video laryngoscope in older children and adults.^{8,9} The size 3 blade is suitable for intubation of adults and children as young as 8 years. Ambu now makes size 1 and 2 blades suitable for intubation of infants and young children. The purpose of this study is to evaluate the performance of the King Vision video laryngoscope in younger patients. Advantages of the King Vision scope include a very high success rate of first pass intubation, relatively low cost (\$11 per intubation) and extreme portability.

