2.0 Rationale and Specific Aims

The purpose of this study is to evaluate the performance characteristics of the King Vision video laryngoscope in pediatric patients between the ages of one month and 10 years of age. If the performance is satisfactory, this device may become a standard laryngoscope for tracheal intubation in elective and emergent tracheal intubations.

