4.0 Enrollment/Randomization

100 patients will be enrolled. Data will be collected from the patients that the King Vision Video Laryngoscope is used. As this is not a comparative study, there shall be no randomization.

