5.0 Study Procedures

All procedures shall be routine procedures for the administration of anesthesia appropriate for the age of the child and the type of surgical procedure. This is a data collection only study .

1. The technique of anesthesia induction will be determined for each patient by the anesthesiologist of record.
2. After the induction of anesthesia, and when the patient is at an adequate depth of anesthesia, tracheal intubation will be performed with the King Vision video laryngoscope by one of the investigators.
3. Data recorded will include gender, age, and weight of the patient.
4. Data specific to the device and tracheal intubation include; size and type of blade (standard vs. channeled), blade tip position, Cormack-Lehane score, tracheal tube size, and a subjective scoring of tracheal tube delivery.
5. See the attached data collection sheet.

6.0 Reporting of Adverse Events or Unanticipated Problems Involving Risk to Participants or Others

We do not anticipate adverse events related to this study. This is a data collections only study therefore there are minimal to no risks to the subjects.

There is a minimal risk of loss of confidentiality. PHI will be accessed for recruitment purposes by the clinical care team and/or research care team.

All data shared with the sponsor will be unidentifiable.

Any reports of adverse events can be made to:

[name]. @ Office number: [contact] or [contact]

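### Having no comparator does not remove the sampling error of a rate from 100 children, and the data sheet does not record whether the King Vision itself completed the intubation

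*Combined protocol and SAP*

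**What the plan says.** The whole analysis plan in the visible text is one sentence in Section 7.0 of the combined protocol and SAP: "As this is not a comparative study, only descriptive statistics will be applied". Section 4.0 sets enrolment at 100 children in a single group, and describes the data set thus: "Data will be collected from the patients that the King Vision Video Laryngoscope is used". Section 2.0 gives the use of the result: "If the performance is satisfactory, this device may become a standard laryngoscope for tracheal intubation in elective and emergent tracheal intubations". No visible passage names a lead measure, an interval or a rate that would count as satisfactory. Section 1.0 comes nearest to naming a measure: "Advantages of the King Vision scope include a very high success rate of first pass intubation".

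On the device, Section 5.0, item 2, says "tracheal intubation will be performed with the King Vision video laryngoscope by one of the investigators" and mentions no other laryngoscope. The INTUBATION box of the data collection sheet (SAP document) nevertheless has two blade fields, one for the King Vision aBlade (1, 2, 2 channeled) and one labelled "Standard laryngoscope blade size" (0 to 3). Below them are one ease-of-passage score, whose worst value (5) means impossible, one attempts row (1 to 3) and one insertion time. An attempt is explained as "Entry of blade into patient's mouth without the need to remove it once entered". Insertion time is explained as "Amount of time from Removal of facemask to the first upstroke of etCO", that is, it ends when exhaled carbon dioxide is first seen. None of these items is labelled by device.

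**The concern.** There are two separate issues.

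**Precision.** The reason given for a purely descriptive analysis is that nothing is being compared. That is a good reason to have no between-group test. It says nothing about how precisely a single-group rate is estimated. If a percentage is reported alone and then called satisfactory, readers may take it as firmer than 100 children can make it, the more so for a complication that happens not to be seen.

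**Attribution.** The procedures name one device and the sheet provides for two. If both blade fields are marked, the sheet does not show which device the attempts and the time belong to, or which one placed the tube. Success can be partly inferred, since a score of 5 marks failure and a carbon dioxide upstroke marks a tube in place, but neither item identifies the blade. First-attempt success with the King Vision could then be counted wrongly. Unlike a missing interval, this cannot be settled from the sheet alone.

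**Working it through.** **Inputs.** n = 100, single group (Section 4.0). The plan gives no expected rate, target, margin or interval width, so the figure of 100 cannot be reproduced, and the observed counts below are assumptions for illustration. Children are treated as independent.

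**Precision.** The exact (Clopper-Pearson) 95% limits for x events in n are:

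- lower = 2.5% quantile of Beta(x, n − x + 1)
- upper = 97.5% quantile of Beta(x + 1, n − x)
- for x = 0, lower = 0 and upper = 1 − 0.025^(1/n)

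| Assumed count | Rate | Exact 95% interval | Width (points) |
|---|---|---|---|
| 95/100 | 95% | 88.7–98.4% | 98.4 − 88.7 = 9.7 |
| 90/100 | 90% | 82.4–95.1% | 95.1 − 82.4 = 12.7 |
| 0/100 | 0% | 0–3.6% | 3.6 |

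For the last row, 1 − 0.025^(1/100) = 0.0362. Wilson intervals agree closely (88.8–97.8% at 95/100 and 82.6–94.5% at 90/100), so the conclusion does not depend on the choice of interval.

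**What the second blade field means.** It could be taken for the non-channeled King Vision blade, because Section 5.0, item 4, calls that type standard. The documents point the other way. The aBlade row already separates 2 from 2 channeled, the second field has different sizes (0 to 3), and Section 1.0 uses the term standard laryngoscope for the conventional device.

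**Attribution.** With 100 children in the denominator, each misclassified child moves the rate by 1/100 = 1 percentage point. There are two directions:

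- *Overstatement.* The King Vision is withdrawn, the standard blade then succeeds at its first entry, and the sheet shows 1. If a of the recorded first-attempt successes arose this way, the true count is the recorded count minus a.
- *Understatement.* The standard blade is tried first, the King Vision then succeeds at its own first entry, and the sheet shows 2. If b children are of this kind, the true count is the recorded count plus b.

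The net error is (a − b)/100. The documents give neither a nor b. Over an assumed range of 0 to 5 children in one direction, the error runs from 0 to 5 points. For example, a recorded 95 with a = 2 is a true 93/100 (86.1–97.1%), and a recorded 93 with b = 2 is a true 95/100 (88.7–98.4%). With a = b = 0 there is no error.

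**The case against.** The case on the other side has weight.

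- **A descriptive plan is legitimate here, and the word does not exclude intervals.** This stands. Where counts are reported, any reader can also add a binomial interval. What remains is that the reason given does not justify leaving intervals out, and none is planned.
- **No rate is named as the main result.** This also stands. Several recorded items are ordinal or continuous, and binomial intervals do not apply to them. First-attempt success is a natural candidate from Section 1.0, but the choice belongs to the investigators.
- **The sheet's own definition works against overstatement.** A child in whom both blades entered the mouth has had at least two entries. A sheet showing 1 would mean that the King Vision entry was left out of a King Vision form. This makes overstatement less likely. It does not remove understatement, and the row still does not say whose entries it counts.
- **The doubtful sheets can be queried.** Each has a subject ID and an investigator field, and Section 10.0 keeps records until analysis is complete. This limits the harm.
- **Some passages were removed, and table layout was lost.** A layout cue or further field cannot be ruled out, so the attribution point applies only to the visible sheet.

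A reader might go further and infer that children were, or will be, switched between devices, or that the resulting bias rivals the sampling error. The documents support neither. They describe no switch and give no count, and any bias scales directly with a number that may be zero.

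**Conclusion.** Both parts hold, at modest size. A rate near 90–95% from 100 children has an exact 95% interval roughly 10 to 13 points wide, and a complication seen in none of them could still have a true rate up to 3.6%. These figures rest on assumed counts and on independence between children. The attribution gap is conditional: 1 percentage point per affected child, in either direction, and nothing if no child had both blades used.

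Three stronger conclusions should not be drawn. Nothing shows that 100 is too few, because the plan states no target to test it against. Section 2.0 raises possible adoption without setting a decision rule, so an undefined meaning of satisfactory is missing detail and not a flawed criterion. And the sheet does not leave success wholly unrecorded, because part of it can be inferred.

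The change is optional. Confidence is high on the intervals and moderate on attribution, because the purpose of the standard-blade field is not stated and some passages are not visible.

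**What to change.** 1. **Section 7.0.** Keep the analysis descriptive, with no between-group tests, and add wording such as: *First-attempt intubation success with the King Vision, among all children in whom it was inserted, and the overall rate of any intubation complication will be reported with exact (Clopper-Pearson) 95% confidence intervals.* The investigators may choose another lead proportion, provided they name it before the data are reviewed.

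2. **Data collection sheet.** Add one line: *Intubation completed with King Vision: Yes / No; if yes, on King Vision attempt no. ___*. This settles both directions of misclassification. It does not divide the insertion time in a child with both blades used, so those times are best listed separately.

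3. **Sheets already collected.** Query only those with both blade fields marked.

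The cost is a sentence or two in Section 7.0, two intervals and one line on the form, with no added patients. Results will look less certain than bare percentages, and the form change is most useful before or early in collection. The sheet line is the more time-sensitive part, since an interval can be added at any time.

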8.0 Privacy/Confidentiality Issue

Data will be kept secure in a password protected database and all paper documentation will be kept in a secure office of the Anesthesia department.

